Coaching of the POFs and provision of performance feedback and tracking to their progress and activities.

Peer-to-Peer Collaboration: The goal of the peer-to-peer collaborations is to provide a community in which POFs can share challenges, lessons learned, and best practices with each other as well as with PHC nurses and leadership.

Training of the HIV clinic nurses on implementation of the TASSH protocol: The HIV nurses will be trained on Identifying, Counseling and Referring (ICR) of adult HIV patients with HTN using the 5 As counseling strategy (Ask, Assess, Advise, Assist and Arrange). Study staff will create a training module for the HIV nurses. Components of the module, including how the 5 As will be mapped onto the ICR approach are outlined below. Table 1 provides a brief summation of module. Eligible patients at the PHCs randomized to the PF intervention will receive the TASSH protocol in the following steps:

Identify HIV patients with uncontrolled HTN: trained HIV nurses will take patients' medical history (whether or not they have a diagnosis of diabetes, heart attack, stroke, heart failure, smoking).

Ask: Create a list of standardized questions that the HIV nurse will ask the patient. Measure patient's BP, if high, then ask the patient if they have been told they have hypertension.

Assess: Based on the BP level, ask additional questions about their weight, height, and their dietary habits. Record the information in the logging report, and refer the patient to the community health center using the reporting/logging system.

Next, they will measure the patients' weight, height, waist circumference and BP with a valid automated device following standard procedures and then conduct lab tests with point-of-care testing on blood glucose, lipids and urine dip stick. The information from the medical history, physical examination and laboratory tests are then used by the nurses to assess patients' CV risk with a validated WHO risk chart. Patients who meet eligibility criteria (<20% CV risk) are scheduled for treatment.

Initiate lifestyle counseling and medication treatment every 1-3 months: The nurses will next counsel eligible patients on lifestyle behaviors for 20 to 30 minutes (increased intake of fruits and vegetables, moderate physical activity and reduce salt intake).

Advise: Counsel the patient on lifestyle behaviors like salt reduction, weight loss, taking BP medications and adoption of a healthy diet.

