Make recommendations to the NHLBI, IRB, and investigators concerning continuation or discontinuation of the trial(s).

Protect the confidentiality of the trial data and the results of monitoring by ensuring that computerized data files (quantitative and qualitative) are password protected. Any back-ups made of the computerized data will be put on separate hard drives which will also be password protected. Only named research staff will have access to the data onsite and offsite.

Implementation of the study protocol will be monitored by the study team in Nigeria, which comprises of the PI in Nigeria and the research staff (i.e. Research Coordinator, Research Assistant), who will be responsible for the monitoring and quality control of the study. The team meets bi-weekly to monitor the study progress, quality of data collection, adherence to the study manual/protocol, and good clinical practice. Study staff will be trained on all study procedures and documentation yearly. The study team will ensure that access to all forms and relevant documents is made available to members of the DSMB upon request, to facilitate their inputs or recommendations on how to improve study activities.

Study Procedure and Assessments

Study Procedures following randomization: After completion of the baseline data collection, all HIV clinics will be randomized in 5 cohorts of 6 clinics every 6 months for 30 months. Upon completion of recruitment of each cohort, the clinics are randomized in a 1:1 ratio to either the PF intervention group or the self-directed group. The randomization sequence will be generated by the study statistician and secured away from the clinics following CONSORT guidelines.

Study Visits: Eligible patients will be identified from the HIV clinics during routine visits. Once eligibility is confirmed, all patients regardless of their group assignment, will have a total of five study visits: baseline, 6, 12 months, 18 months, and 24 months post randomization. The structure of each study visit and the respective measures will be the same for each group (see study measures below). Beginning with the baseline visit, an average of 3 BP readings will be used as the measure for each study visit. The same procedure will be repeated at 6-, 12-, 18- and 24-month study visits.

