Follow-up Study Visits (6, 12, 18, and 24 months): The research coordinator (RC) will meet with each patient to collect follow up data on primary outcome measure (BP measurements identical to that described for the baseline visit) and secondary outcomes. Study measures for both groups are similar and will be conducted in the same manner by the RC. Patients in the HIV clinics randomized to the Self-Directed Group will attend follow up study visits as scheduled while those in the clinics randomized to the PF Intervention will meet with their nurses every three months [for lifestyle counseling and treatment] in addition to the scheduled study visits.

On-time Follow-up Study Visits (6, 12, 18, and 24 months): On-time visit occurs within a +/- 3-months window of the expected follow-up date. For the 6-month follow-up visit, an on-time visit occurs between 3 and 9 months after baseline visit. For the 12-month visit, an on-time visit occurs between 9 and 15 months. For the 18-month visit, an on-time visit occurs between 15 and 21 months.

Baseline visits: The RC will confirm eligibility status and obtain informed consent from each patient. At baseline, we will measure the organizational and individual-level factors shown to affect implementation of evidence-based practices, including leadership, organizational capacity to change, individual attitudes toward evidence-based practices, and the degree of buy-in among practice facilitators.

SECTION 6: Study Measures

Primary Outcome: Change in systolic BP from baseline to 12 months. The SBP reduction in patients will be assessed as mean change in systolic BP from baseline to 12 months.

Secondary Outcomes are:

Adoption [proportion of patients who were correctly diagnosed with HTN, received lifestyle counseling and antihypertensive treatment]; and *sustainability* [maintenance of TASSH uptake at the HIV clinics at 24 months].

The mediators of TASSH across the HIV clinics at 12 and 24 months.

Assessment of Outcome Measures:

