Adverse Events and Serious Adverse Events: Important medical events are those that may not be immediately life threatening, but are clearly of major clinical significance. They may jeopardize the subject, and may require intervention to prevent one of the other serious outcomes noted above. All adverse events that do not meet any of the criteria for serious should be regarded as non-serious adverse events.

Adverse Event: An adverse event (AE) is any symptom, sign, illness or experience that develops or worsens in severity during the course of the study. Intercurrent illnesses or injuries should be regarded as adverse events if they increase in severity or frequency during the course of the study. Abnormal results of diagnostic procedures are considered to be adverse events if the abnormality meets any of the following criteria:

- results in study withdrawal;
- is associated with a serious adverse event;
- is associated with clinical signs or symptoms;
- leads to additional treatment or to further diagnostic tests; or
- is considered by the investigator to be of clinical significance.

Serious Adverse Event: A serious adverse event is any AE that meets the following criteria:

- fatal;
- life-threatening;

- requires or prolongs hospital stay (Hospitalisation for elective treatment of a pre-existing condition (known or diagnosed prior to informed consent signature) that did not worsen from baseline is NOT considered an SAE).
- results in persistent or significant disability or incapacity;
- a congenital anomaly or birth defect; or
- an important medical event

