Assessment of Adverse Events: Participants will be evaluated for AEs at each study visit by the HIV nurse. Adverse events identified on the field will be reported to the study team immediately. A form will be completed by the study team to capture the relevant information. The study team will report the serious adverse events to the NIMR IRB. SAEs will also be reported to the LSPHB, to the Chair of the DSMB as well as to the sponsor. The DSMB has the authority to halt the implementation if it perceives that harm is occurring due to the intervention. Summaries of adverse events reports will be made to NIH in the yearly progress report or, at the end of year 5, in the final report, unless the nature of a particular event is such that it bears reporting to NIH immediately. Events will be followed for outcome information until resolution, stabilization, or until the subject completes the study. Subjects will be questioned regarding changes in their health and medications. Additionally, the subjects' overall health will be monitored as part of routine standard of care by community nurse; any changes to the subject's health will be noted in the subject's research record.

Time Period and Frequency for Adverse Event Assessment and Follow-Up: AEs will be recorded from the time the subject signs the informed consent through the subject's completion of the study. Events will be followed for outcome information until resolution, stabilization, or until the subject completes the study. All unresolved adverse events will be monitored by the investigator until the events are resolved, the post-study reporting period has ended, the subject is lost to follow-up, or the AE is otherwise explained. At the last scheduled visit, the investigator should instruct each subject to report any subsequent event(s) that the subject, or the subject's personal physician, believes might reasonably be related to participation in this study. Any death or adverse event occurring at any time after a subject has discontinued or terminated study participation that may reasonably be related to this study should be recorded in the subject's study chart and reported to applicable regulatory agencies according to current guidelines.

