Identifying HIV clinics: The NIMR will be responsible for all recruitment activities. NIMR has deep connections with the Lagos State Healthcare Board and its network of over 67 HIV clinics in Lagos, Nigeria given its previous work with these organizations. Currently, there are over 67 clinics affiliated with NIMR; we will recruit 30 HIV clinics for this study. Two Research Coordinators (RC) will be hired by NIMR to conduct the screening, consent, enrollment, and all study assessments. [name] will supervise recruitment and retention activities of the research staff.

Recruitment of HIV Clinics: We will recruit HIV clinics that are affiliated with the Lagos State Primary Health Care Board, which is also affiliated with the Lagos State AIDS Control Agency (LSACA). [name] will meet with clinic leaders to provide study overview. All eligible HIV clinics must be a NIMR-affiliated clinic - there are 67 across Lagos. Eligible clinics will be selected from areas geographically distinct from one another with equal urban/rural mix. Once a clinic agrees to participate, their key leadership personnel will be asked to sign a MOU and identify 2 nurses to be trained to deliver TASSH.

Participant recruitment strategy: The RCs will work with nurses to develop a recruitment strategy specific to the clinic. Once the nurse has identified a participant who meets the inclusion criteria, the person is given a telephone number of the RC to call if they are interested in the study. During the call, the RC will give a brief explanation of the procedures, including the following: that participants will have a 50-50 chance of being in the Practice Facilitation Strategy or Self-Directed Condition (depending on which group their clinic is randomized to); that not every participant is accepted into the study (this will be decided during the screening visit). If the person desires to participate at this point, an in-person appointment for the consent/screening visit is then set for the participant with the RC and nurse.

Characteristics of the study population during the pre-implementation and Implementation phase

Pre-implementation phase

This phase will involve 70 participants, who are steering committee members, key stakeholder or user testers (Nurses, physicians, patient advocate, Directors HIV clinics). Eligibility criteria for study participants are outlined below.

Inclusion criteria

- Be an adult aged 18 years and older.
- Ability to provide consent.

Exclusion criteria

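### Adverse event counts are open to unequal ascertainment if compared by arm: HIV nurses assess them, only practice facilitation patients have extra scheduled nurse contacts, and the source of an event is not recorded

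*Combined protocol and SAP*

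**What the plan says.** **Who assesses.** Section 6 (Assessment of Adverse Events): "Participants will be evaluated for AEs at each study visit by the HIV nurse". The data collection paragraph later in that section also has HIV nurses collecting data. Against this, Section 10 (Identifying HIV clinics) says that two research coordinators "will be hired by NIMR to conduct the screening, consent, enrollment, and all study assessments". Section 3 (Strategies for Recruitment and Retention) says the same of the research staff, and Section 5 (Follow-up Study Visits) has the coordinator collect follow-up data in the same way in both arms.

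**When.** Section 5 gives every patient "five study visits: baseline, 6, 12 months, 18 months, and 24 months post randomization" and adds: "The structure of each study visit and the respective measures will be the same for each group". Patients in PF clinics also "will meet with their nurses every three months [for lifestyle counseling and treatment] in addition to the scheduled study visits".

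**What else enters the record.** Section 6: "Adverse events identified on the field will be reported to the study team immediately". Recording runs from consent to completion, and health changes noticed by the community nurse in routine care go into the research record; neither statement distinguishes the arms. An abnormal diagnostic result counts as an AE if it meets any of five criteria, one of which reads "leads to additional treatment or to further diagnostic tests; or". The TASSH steps that Section 4 describes for PF clinics have nurses "conduct lab tests with point-of-care testing on blood glucose, lipids and urine dip stick".

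**Who uses it.** The DSMB may stop implementation if it judges the intervention to be causing harm, and it receives AE reports at twice-yearly meetings (Section 6). The one between-arm signal named among its duties (Section 5) is a worsening of BP control or cardiovascular risk in the intervention arm relative to control.

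**The concern.** In an open-label trial, AE counts can be compared between arms only if both arms are asked the same questions, equally often, over the same recall period. Here the assessor named for AEs is also the person who delivers the intervention, and PF patients have more scheduled meetings with that person. Because field-identified events are accepted at any time, what is noticed at a PF-only meeting can enter the same count as what is asked at a common study visit.

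At stake is the safety information that reaches the DSMB. To attribute harm to the intervention in a two-arm trial, one naturally looks at the other arm. If PF counts are raised because more is detected, a real excess cannot be told apart from extra detection.

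**Working it through.** **Plan's own figures.** The documents give no AE rate and no planned AE comparison, so there is none to reproduce. The sample size is consistent: 30 clinics × 32 patients = 960, and 15 × 32 = 480 per arm.

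**Step 1: scheduled contacts after baseline, to month 12** (Section 5)

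| Arm | Months | Contacts |
|---|---|---|
| Self-directed, study visits | 6, 12 | 2 |
| PF, quarterly meetings coinciding with study visits | 3, 6, 9, 12 | 4 |
| PF, quarterly meetings on separate dates | 2 study visits + 4 meetings | 6 |

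The 2 counts scheduled study visits only. Self-directed patients also attend routine clinic care, at a frequency the documents do not give. Section 4 states a one-to-three-month interval for counselling and treatment, against three months in Section 5, so the PF count is itself uncertain.

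**Step 2: share of events detected.** Assume equal true rates, and that a transient event is reported only if it occurred within *w* months before a contact. With contacts every *s* months, share = min(*w*, *s*)/*s*. Here *s* = 6 for self-directed and *s* = 3 for PF in the coincident case. I also assume that everything noticed at a quarterly meeting enters the AE data.

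| *w* (assumed) | Self-directed | PF | Ratio |
|---|---|---|---|
| 1 month | 1/6 = 0.167 | 1/3 = 0.333 | 2.0 |
| 3 months | 3/6 = 0.500 | 3/3 = 1.000 | 2.0 |
| 4 months | 4/6 = 0.667 | 1.000 | 1.5 |
| 6 months | 6/6 = 1.000 | 1.000 | 1.0 |

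Separate meeting dates could take the ratio above 2.0 when recall is short, towards 6/2 = 3.0 where recall windows do not overlap. If only events from the common visits are compared, the ratio is 1.0 whatever the recall.

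**Step 3: could this look like a safety signal?** Take 480 per arm and divide by the design effect 1 + 31 × ICC. This gives effective *n* = 480, 480/1.31 = 366 and 480/2.55 = 188 for ICC 0, 0.01 and 0.05. The chance of a two-sided p < 0.05 is Φ{(|p₁ − p₂| − 1.96√[2p̄(1 − p̄)/n]) / √[(p₁(1 − p₁) + p₂(1 − p₂))/n]}, where p₁ and p₂ are the true risk times the shares above. True risk and ICC are assumptions.

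| True 12-month risk | *w* | Detected, self-directed v PF | Chance at ICC 0 / 0.01 / 0.05 |
|---|---|---|---|
| 10% | 1 | 1.7% v 3.3% | 38% / 30% / 18% |
| 20% | 1 | 3.3% v 6.7% | 66% / 54% / 32% |
| 20% | 3 | 10% v 20% | 99% / 97% / 78% |
| 20% | 6 | 20% v 20% | no distortion |

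**Step 4: abnormal test results.** The AE definition is generic: it neither names nor excludes results of TASSH testing. A glucose, lipid or urine finding that led to treatment or further tests could meet a listed criterion. Whether it would be recorded as an AE is not stated.

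**The case against.** The case on the other side is substantial.

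- **Formal AE evaluation is tied to study visits, which are the same in both arms.** This stands. Any imbalance has to come through field-identified events, so 4 against 2 counts nurse contacts and not scheduled AE assessments.
- **No by-arm AE table, test or stopping threshold is described.** This also stands. A reader might infer that the DSMB's decision rests on a biased arm comparison, but the documents specify no such comparison. The one between-arm example concerns BP control and cardiovascular risk, and the coordinator measures BP on the same schedule in both arms.
- **Self-directed patients are not confined to study visits.** They receive their facility's standard care, and the routine-care channel in Section 6 applies to both arms. This narrows the gap by an unknown amount.
- **The screening argument is an inference.** A reader might infer that TASSH testing will generate AEs mainly in PF clinics. But an AE must appear or get worse during the study, the laboratory tests belong to a risk assessment made before treatment is scheduled, and no repeat testing is stated. Raised BP is not specific to PF: it is an entry criterion, and self-directed nurses are trained on the 5As, which include measuring BP, and on referral.
- **The direction is not certain.** Nurses whose performance is under review might report fewer events. Deaths and hospital stays probably depend little on contact frequency.

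What remains is the conflict over the assessor, the PF-only scheduled contacts, and the absence of any rule separating events found there from those found at common visits. The AE form is not reproduced in the document, so it may already record the source; the protocol does not require it.

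**Conclusion.** The concern holds as a risk, not as a demonstrated bias. AE capture is open to differential ascertainment if counts are compared by arm. Under the assumptions shown, with meetings coinciding with study visits, the distortion runs from nil (ratio 1.0, full recall over six months) to a doubling (ratio 2.0, recall of three months or less). The documents state neither the recall period nor whether findings at quarterly meetings enter the AE data, so no single figure can be defended. The text does not support saying that PF will show more AEs, or that the halt decision is biased. The correction is cheap and protects the data the DSMB will see, so it is worth making. The conflict over who assesses AEs needs reconciling in any case.

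**What to change.** 1. Reconcile Section 6 with Sections 3, 5 and 10, so that the research coordinator asks the same AE questions, with the same recall period, at the 6-, 12-, 18- and 24-month visits in both arms. Align the list in Section 2 (Assessment of Potential Risks and Benefits), which omits month 18.
2. Record the source of each AE: common study visit, PF quarterly contact or routine care.
3. Keep immediate reporting of all field-identified events and SAEs.
4. Give the DSMB by-arm tables of common-visit AEs plus all SAEs. Show between-visit events, and any abnormal results found through TASSH testing, in a separate table. They should not be left out, since worsening BP or cardiovascular risk is the harm signal that Section 5 names.

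**Cost.** Wording changes, a few questions at visits the coordinators already run, one field on the AE form and a second AE table. No extra visits are needed.

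**Limit.** Section 4 says that coordinators cannot be blinded either. The change equalises the schedule and the questions but does not remove the assessor's knowledge of the arm.
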